10.6. Appendix 6: Liver Safety: Suggested Actions and Follow-up Assessments

Potential Cases of Drug-Induced Liver Injury

Humans exposed to a drug who show no sign of liver injury (as determined by elevations in transaminases) are termed “tolerators,” while those who show transient liver injury, but adapt are termed “adaptors.” In some participants, transaminase elevations are a harbinger of a more serious potential outcome. These participants fail to adapt and therefore are “susceptible” to progressive and serious liver injury, commonly referred to as drug-induced liver injury (DILI). Participants who experience a transaminase elevation above 3 times the upper limit of normal (\times ULN) should be monitored more frequently to determine if they are an “adaptor” or are “susceptible.”

In the majority of DILI cases, elevations in aspartate aminotransferase (AST) and/or alanine aminotransferase (ALT) precede total bilirubin (TBili) elevations ($>2 \times$ ULN) by several days or weeks. The increase in TBili typically occurs while AST/ALT is/are still elevated above $3 \times$ ULN (ie, AST/ALT and TBili values will be elevated within the same laboratory sample). In rare instances, by the time TBili elevations are detected, AST/ALT values might have decreased. This occurrence is still regarded as a potential DILI. Therefore, abnormal elevations in either AST OR ALT in addition to TBili that meet the criteria outlined below are considered potential DILI (assessed per Hy’s law criteria) cases and should always be considered important medical events, even before all other possible causes of liver injury have been excluded.

The threshold of laboratory abnormalities for a potential DILI case depends on the participant’s individual baseline values and underlying conditions. Participants who present with the following laboratory abnormalities should be evaluated further as potential DILI (Hy’s law) cases to definitively determine the etiology of the abnormal laboratory values:

- Participants with AST/ALT and TBili baseline values within the normal range who subsequently present with AST OR ALT values $>3 \times$ ULN AND a TBili value $>2 \times$ ULN with no evidence of hemolysis and an alkaline phosphatase value $<2 \times$ ULN or not available.
- For participants with baseline AST **OR** ALT **OR** TBili values above the ULN, the following threshold values are used in the definition mentioned above, as needed, depending on which values are above the ULN at baseline:
 - Preexisting AST or ALT baseline values above the normal range: AST or ALT values >2 times the baseline values AND $>3 \times$ ULN; or $>8 \times$ ULN (whichever is smaller).
 - Preexisting values of TBili above the normal range: TBili level increased from baseline value by an amount of at least $1 \times$ ULN **or** if the value reaches $>3 \times$ ULN (whichever is smaller).

Rises in AST/ALT and TBili separated by more than a few weeks should be assessed individually based on clinical judgment; any case where uncertainty remains as to whether it represents a potential Hy's law case should be reviewed with the sponsor.

The participant should return to the investigator site and be evaluated as soon as possible, preferably within 48 hours from awareness of the abnormal results. This evaluation should include laboratory tests, detailed history, and physical assessment.

In addition to repeating measurements of AST and ALT and TBili for suspected cases of Hy's law, additional laboratory tests should include albumin, creatine kinase (CK), direct and indirect bilirubin, gamma-glutamyl transferase (GGT), prothrombin time (PT)/international normalized ratio (INR), total bile acids, and alkaline phosphatase. Consideration should also be given to drawing a separate tube of clotted blood and an anticoagulated tube of blood for further testing, as needed, for further contemporaneous analyses at the time of the recognized initial abnormalities to determine etiology. A detailed history, including relevant information, such as review of ethanol, acetaminophen (either by itself or as a coformulated product in prescription or over-the-counter medications), recreational drug, supplement (herbal) use and consumption, family history, sexual history, travel history, history of contact with a jaundiced person, surgery, blood transfusion, history of liver or allergic disease, and potential occupational exposure to chemicals, should be collected. Further testing for acute hepatitis A, B, C, D, and E infection and liver imaging (eg, biliary tract) and collection of serum sample for acetaminophen drug and/or protein adduct levels may be warranted.

All cases demonstrated on repeat testing as meeting the laboratory criteria of AST/ALT and TBili elevation defined above should be considered potential DILI (Hy's law) cases if no other reason for the liver function test (LFT) abnormalities has yet been found. **Such potential DILI (Hy's law) cases are to be reported as SAEs, irrespective of availability of all the results of the investigations performed to determine etiology of the LFT abnormalities.**

A potential DILI (Hy's law) case becomes a confirmed case only after all results of reasonable investigations have been received and have excluded an alternative etiology.

10.7. Appendix 7: ECG Findings of Potential Clinical Concern

ECG Findings That May Qualify as Adverse Events (AEs)

 Marked sinus bradycardia (rate <40 bpm) lasting minutes. New PR interval prolongation >280 msec. New prolongation of QTcF to >480 msec (absolute) or by \geq60 msec from baseline. New-onset atrial flutter or fibrillation, with controlled ventricular response rate: ie, rate <120 bpm. New-onset type I second-degree (Wenckebach) AV block of >30 seconds' duration. Frequent premature ventricular complexes (PVCs), triplets, or short intervals (<30 seconds) of consecutive ventricular complexes.
ECG Findings That May Qualify as Serious Adverse Events (SAEs)

 QTcF prolongation >500 msec. New ST-T changes suggestive of myocardial ischemia. New-onset left bundle branch block (QRS >120 msec). New-onset right bundle branch block (QRS >120 msec). Symptomatic bradycardia. Asystole: 
 In awake, symptom-free patients in sinus rhythm, with documented periods of asystole \geq3.0 seconds or any escape rate <40 bpm, or with an escape rhythm that is below the AV node; In awake, symptom-free patients with atrial fibrillation and bradycardia with 1 or more pauses of at least 5 seconds or longer; Atrial flutter or fibrillation, with rapid ventricular response rate: rapid = rate >120 bpm. Sustained supraventricular tachycardia (rate >120 bpm) ("sustained" = short duration with relevant symptoms or lasting >1 minute).

- Ventricular rhythms >30 seconds' duration, including idioventricular rhythm (rate <40 bpm), accelerated idioventricular rhythm (40< x <100), and monomorphic/polymorphic ventricular tachycardia >100 bpm (such as torsades de pointes).
- Type II second-degree (Mobitz II) AV block.
- Complete (third-degree) heart block.

ECG Findings That Qualify as Serious Adverse Events

- Change in pattern suggestive of new myocardial infarction.
- Sustained ventricular tachyarrhythmias (>30 seconds' duration).
- Second- or third-degree AV block requiring pacemaker placement.
- Asystolic pauses requiring pacemaker placement.
- Atrial flutter or fibrillation with rapid ventricular response requiring cardioversion.
- Ventricular fibrillation/flutter.
- At the discretion of the investigator, any arrhythmia classified as an adverse experience.

The enumerated list of major events of potential clinical concern are recommended as “alerts” or notifications from the core ECG laboratory to the investigator and Pfizer study team, and not to be considered as all inclusive of what to be reported as AEs/SAEs.

10.8. Appendix 8: 2010 ACR/EULAR Classification Criteria for Rheumatoid Arthritis (RA)

Presented below are the 2010 American College of Rheumatology (ACR)/European League Against Rheumatism (EULAR) classification criteria for RA.

Target population (Who should be tested?) must have:

1. Have at least 1 joint with definite clinical synovitis (swelling).*
2. With the synovitis not better explained by another disease.†

Classification criteria for RA (score-based algorithm: add score of categories A–D;

a score of $\geq 6/10$ is needed for classification of a patient as having definite RA):

A. Joint involvement§	SCORE (A) _____
1 large joint¶	0
2-10 large joints	1
1-3 small joints (with or without involvement of large joints)#+	2
4-10 small joints (with or without involvement of large joints)	3
>10 joints (at least 1 small joint)**	5

B. Serology (at least 1 test result is needed for classification)††	SCORE (B) _____
Negative RF and negative ACPA	0
Low-positive RF or low-positive ACPA	2
High-positive RF or high-positive ACPA	3

C. Acute-phase reactants (at least 1 test result is needed for classification) 	SCORE (C)
Normal CRP and normal ESR	0
Abnormal CRP or abnormal ESR	1

D. Duration of symptoms §§	SCORE (D) _____
<6 weeks	0
≥6 weeks	1

TOTAL SCORE (A+B+C+D)

PFIZER CONFIDENTIAL

A TOTAL Score of $\geq 6/10$ is needed for classification of a patient as having definite RA)[‡]

* The criteria are aimed at classification of newly presenting patients. In addition, patients with erosive disease typical of rheumatoid arthritis (RA) with a history compatible with prior fulfillment of the 2010 criteria should be classified as having RA. Patients with longstanding disease, including those whose disease is inactive (with or without treatment) who, based on retrospectively available data, have previously fulfilled the 2010 criteria should be classified as having RA.

† Differential diagnoses vary among patients with different presentations, but may include conditions such as systemic lupus erythematosus, psoriatic arthritis, and gout. If it is unclear about the relevant differential diagnoses to consider, an expert rheumatologist should be consulted.

‡ Although patients with a score of $<6/10$ are not classifiable as having RA, their status can be reassessed and the criteria might be fulfilled cumulatively over time.

§ Joint involvement refers to any *swollen* or *tender* joint on examination, which may be confirmed by imaging evidence of synovitis. Distal interphalangeal joints, first carpometacarpal joints, and first metatarsophalangeal joints are *excluded from assessment*. Categories of joint distribution are classified according to the location and number of involved joints, with placement into the highest category possible based on the pattern of joint involvement.

¶ “Large joints” refers to shoulders, elbows, hips, knees, and ankles.

“Small joints” refers to the metacarpophalangeal joints, proximal interphalangeal joints, second through fifth metatarsophalangeal joints, thumb interphalangeal joints, and wrists.

** In this category, at least 1 of the involved joints must be a small joint; the other joints can include any combination of large and additional small joints, as well as other joints not specifically listed elsewhere (eg, temporomandibular, acromioclavicular, sternoclavicular, etc.).

†† Negative refers to IU values that are less than or equal to the upper limit of normal (ULN) for the laboratory and assay; low-positive refers to IU values that are higher than the ULN but ≤ 3 times the ULN for the laboratory and assay; high-positive refers to IU values that are >3 times the ULN for the laboratory and assay. Where rheumatoid factor (RF) information is only available as positive or negative, a positive result should be scored as low-positive for RF. ACPA= anti-citrullinated protein antibody.

‡‡ Normal/abnormal is determined by local laboratory standards. CRP = C-reactive protein; ESR = erythrocyte sedimentation rate.

§§ Duration of symptoms refers to patient self-report of the duration of signs or symptoms of synovitis (eg, pain, swelling, tenderness) of joints that are clinically involved at the time of assessment, regardless of treatment status.

10.9. Appendix 9: Criteria for Classification of Functional Status in Rheumatoid Arthritis

Class I: Completely able to perform usual activities of daily living (self-care, vocational, and avocational).

Class II: Able to perform usual self-care and vocational activities but limited in avocational activities.

Class III: Able to perform usual self-care activities but limited in vocational and avocational activities.

Class IV: Limited in ability to perform usual self-care, vocational, and avocational activities.

Usual self-care activities including dressing, feeding, bathing, grooming, and toileting. Avocational (recreational and/or leisure) and vocational (work, school, homemaking) activities are patient-desired and age- and sex-specific.

10.10. Appendix 10: Disease Activity Score DAS (DAS28-CRP), **CCI** Assessments

The formula for calculation of DAS28-CRP uses the following 4 components:

- Swollen Joints (0–28);
- Tender Joints (0–28);
- hsCRP (high sensitivity C-reactive protein);
- Patient's Global Assessment (PtGA) of Arthritis (0 – 100 mm VAS).

DAS28-CRP= $0.56 \sqrt{(\text{DAS 28 tender joint count})} + 0.28 \sqrt{(\text{DAS 28 swollen joint count})} + 0.36 \ln(\text{CRP [mg/L]} + 1) + 0.014 (\text{PtGA [mm]}) + 0.96$.

CCI

10.11. Appendix 11: Prohibited Concomitant Medications

Prohibited Concomitant Medications

Please note that this list addresses only CYP3A4 inhibitors and inducers, CYP3A substrates and BCRP and Pgp substrates. This is not an all-inclusive list. Study personnel should stay current and consult with their pharmacy to exclude all concomitant medications that are either moderate to potent CYP3A inhibitors or inducers or sensitive or moderate sensitive CYP3A4 substrates or BCRP or Pgp substrates with narrow therapeutic index.

Moderate to Potent CYP3A Inhibitors*		Moderate to Potent CYP3A Inducers**
Amprenavir	Indinavir#	Avasimibe#
Amiodarone	Itraconazole#	Bosentan
Aprepitant	Ketoconazole#	Barbiturates
Atazanavir	Lopinavir#	Carbamazepine#
Boceprevir	Mibefradil#	Efavirenz
Casopitant	Mifepristone (RU486)	Etravirine
Cimetidine	Nefazodone#	Mitotane#
Ciprofloxacin	Nelfinavir#	Modafinil
Clarithromycin#	Norfloxacin	Nafcillin
Cobicistat#	Posaconazole#	Phenobarbital#
Conivaptan#	Ritonavir#	Phentytoin#
Darunavir	Saquinavir#	Rifabutin#
Diethyldithiocarbamate	Schisandra sphenanthera	Rifampin #
Diltiazem	Telaprevir	St. John's Wort#
Dronedarone	Telithromycin#	Talviraline
Elvitegravir#	Tipranavir#	
Erythromycin	Tofisopam	
Fluconazole	Troleandomycin#	
Fluvoxamine	Verapamil	
Imatinib	Voriconazole#	
Danoprevir	Crizotinib	
Grapefruit Juice***	Faldepravir	
Idelalisib	Netupitant	
Nilotinib	Isavuconazole	
CYP3A4 Substrates##		Pgp Substrates
Aprepitant	Argatroban	Digoxin
Eliglustat	Alfentanil	
Pimozide	Astemizole	BCRP Substrates
Conivaptan	Cisapride	Rosuvastatin
Darunavir	Cyclosporine	Glecaprevir
Dasatinib	Diergotamine	Pibrentasvir
Dronedarone	Ergotamine	
Ebastine	Fentanyl	
Indinavir	Quinidine	
Lomitapide	Terfenadine	
Nisoldipine	Valproate	
Rilpivirine		

Saquinavir		
Sirolimus		
Tacrolimus		
Tipranavir		
Tolvaptan		

- * All prohibited drugs that are CYP3A inhibitors require at least a 7 day or 5 half-lives (whichever is longer) washout prior to the first dose of study drug. Note: Amiodarone requires discontinuation at least 290 days (~5 half-lives, half-life averages ~58 days) prior to the first dose of study drug.
- ** All prohibited drugs that are CYP3A inducers require at least a 28 day or 5 half-lives (whichever is longer) washout prior to the first dose of study drug.
- # Notated as potent inhibitors or inducers.
- ## The label recommends to avoid (or contraindicate) use of these concomitant medication with moderate CYP3A4 inhibitors (eg, PF-06651600).
- ***It is recommended that study participants avoid consumption of grapefruit juice exceeding 8 ounces (~240 ml) total in a day while in the study.

In a situation where appropriate medical care of a subject requires the use of a prohibited CYP3A inhibitor or inducer: Moderate to potent inhibitors and inducers of CYP3A are not permitted in the study EXCEPT in emergency situations requiring no more than one day of administration. **Note: Amiodarone and mitotane are not permitted for any duration due to their long half-lives.** Topical (including skin or mucous membranes) application of antimicrobial and antifungal medications is permitted.

Concomitant Medications to be Used with Caution or Dose Reduction

CYP3A4 Substrates (Use with caution or dose reduction) [§]	
Alprozolam	Midazolam
Atorvastatin	Naloxegol
Colchicine	Quetiapine
Tadalafil	Sildenafil
Alfentanil	Simvastatin
Avanafil	Triazolam
Budesonide	Vardenafil
Buspirone	Fentanyl
Eletriptan	Tramadol
Eplerenone	Oxycodone
Everolimus	Hydrocodone
Felodipine	Codeine
Ibrutinib	Dihydrocodeine
Lovastatin	Buprenorphine
Lurasidone	Methadone
Maraviroc	Rivaroxaban [§]

[§] The label allows to use concomitant medication with moderate CYP3A4 inhibitors with caution or dose adjustment. Also, the drug will not affect PF-06651600 exposure (either no effect or weak CYP3A4 inhibitor).

[§] The label recommends to avoid use of the drug in multiple conditions (for example, avoid use in patients with CrCl 15 to <80 mL/min who are receiving concomitant combined P-gp and moderate CYP3A4 inhibitors). Clinical judgement should be used in co-administration.

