5. STUDY POPULATION

This study can fulfill its objectives only if appropriate participants are enrolled. The following eligibility criteria are designed to select participants for whom participation in the study is considered appropriate. All relevant medical and nonmedical conditions should be taken into consideration when deciding whether a particular participant is suitable for this protocol.

Prospective approval of protocol deviations to recruitment and enrollment criteria, also known as protocol waivers or exemptions, is not permitted.

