7. Participants must have been taking oral MTX (or equivalent parenteral MTX) at an adequate dose (generally between 15 and 25 mg weekly [inclusive] unless documented to be intolerant to these doses) and for a sufficient duration (generally at least 3 months but may be as short as at least 8 weeks if consistent with local standard of care treatment guidelines) prior to Screening (Visit 1). To determine that the participant had an inadequate response to MTX, defined, for the purpose of this study, by the investigator's and participant's opinions that the participant did not experience adequate benefit from MTX plus the presence of sufficient residual disease activity to meet the entry criteria. Current treatment with methotrexate is not required for participant eligibility, provided documentation of prior inadequate response to or intolerance of MTX is available and provided in source documentation.
8. Participants receiving non-prohibited concomitant medications for any reason must be on a stable regimen, which is defined as not starting a new drug or changing dosage within 7 days or 5 half-lives (whichever is longer) prior to first study dose.

Weight:

9. Body weight must be >40 kg.

Informed Consent:

10. Capable of giving signed informed consent as described in [Appendix 1](#) ([Section 10.1](#)), which includes compliance with the requirements and restrictions listed in the informed consent document (ICD) and in this protocol.

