5.3. Randomization Criteria

Participants must meet all [inclusion/exclusion criteria](#) as well as all criteria for concomitant medications (including stability criteria) at time of randomization.

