6.5.3. Prohibited Concomitant Medications

6.5.3.1. Strong and Moderate Inhibitors and Inducers of CYP3A4

Systemic therapy with medications that are strong or moderate CYP3A4 inhibitors, strong CYP3A inducers (some common examples are provided in [Appendix 11](#)) are prohibited within 4 weeks or 5 half-lives (whichever is longer) prior to the Randomization Visit (Visit 2) and during the trial.

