6.5.3.3. Substrates of CYP3A4

The exposure of CYP3A4 substrates may increase when co-administered with PF-06651600. The use of drugs primarily metabolized and cleared by CYP3A4 should be either avoided within 4 weeks or 5 half-lives (whichever is longer) prior to the Randomization Visit (Visit 2) and during the trial or used with caution using clinical judgement. Please follow the respective approved prescribing guidelines (some common examples are provided in [Appendix 11](#)).

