6.5.3.4. Substrates of BCRP

The exposure of substrates of BCRP substrates may increase when co-administered with PF-06650833. The use of BCRP substrates listed in [Appendix 11](#) is prohibited within 4 weeks or 5 half-lives (whichever is longer) prior to the Randomization Visit (Visit 2) and during the trial. Other BCRP substrates should be used with caution using clinical judgement. Please follow the respective approved prescribing guidelines (some common examples are provided in [Appendix 11](#)).

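### Appendix 11 states a shorter CYP3A inhibitor washout than Section 6.5.3.1, and lists alfentanil and fentanyl as both prohibited and usable with caution (minor).

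*Protocol*

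**What the plan says.** **Washout.** Protocol Section 6.5.3.1 covers strong or moderate CYP3A4 inhibitors and strong CYP3A inducers. It says that they "are prohibited within 4 weeks or 5 half-lives (whichever is longer) prior to the Randomization Visit (Visit 2) and during the trial", and refers to Appendix 11 for examples. The Appendix 11 footnote on inhibitors says: "All prohibited drugs that are CYP3A inhibitors require at least a 7 day or 5 half-lives (whichever is longer) washout", counted back from the first dose. The footnote on inducers directly below it says: "All prohibited drugs that are CYP3A inducers require at least a 28 day or 5 half-lives (whichever is longer) washout". That figure agrees with Section 6.5.3.1.

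Section 5.3 requires participants to meet the inclusion and exclusion criteria "as well as all criteria for concomitant medications (including stability criteria) at time of randomization". Section 5 adds: "Prospective approval of protocol deviations to recruitment and enrollment criteria, also known as protocol waivers or exemptions, is not permitted".

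**Opioids.** Alfentanil and fentanyl are in the Appendix 11 prohibited table under CYP3A4 substrates. The note there says that labelling advises against, or contraindicates, use with moderate CYP3A4 inhibitors, and names PF-06651600 as an example. Both drugs are also in the later table of drugs to be used with caution or at a reduced dose. Its note says that labelling allows such use.

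In the body text, Section 6.5.3.3 says that CYP3A4 substrates "should be either avoided within 4 weeks or 5 half-lives (whichever is longer) prior to the Randomization Visit (Visit 2") and during the trial, or else used with caution on clinical judgement. Section 6.5.2.3 allows stable background opioids only if they are not prohibited, up to the equivalent of 20 mg oral morphine.

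**The concern.** An eligibility rule should give one answer wherever a site looks it up. A coordinator who checks a drug against the Appendix 11 list meets a complete rule beside it, with its own longer-of-two clause and no pointer back to Section 6.5.3.1. Because the inducer footnote says 28 days, the 7-day figure can look like a deliberate concession for inhibitors. At stake are inconsistent eligibility decisions between sites and avoidable deviations that cannot be waived in advance.

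For the two opioids, the two lists give opposite answers. Opioid use is expected in this trial (Sections 6.5.1 and 6.5.2.3), and two of the five arms contain PF-06651600. Treatment is blinded, so a site cannot adjust its caution by arm. It needs to know whether a participant already on fentanyl can be enrolled and continue.

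**Working it through.** **Inputs for the washout**

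- Rule A, Section 6.5.3.1: the longer of 28 days and 5 half-lives before Visit 2.
- Rule B, Appendix 11 inhibitor footnote: the longer of 7 days and 5 half-lives before the first dose.
- Anchor: the Schedule of Activities puts randomization and the first administration both at Visit 2, Day 1. The different reference points therefore do not explain the gap.
- Half-life: the documents give one for a single listed inhibitor, amiodarone, at about 58 days.

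**The plan's own figure.** 5 x 58 = 290 days, as the footnote states. For amiodarone, A = max(28, 290) = 290 and B = max(7, 290) = 290, so the rules agree.

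**General case.** With half-life t in days, A = max(28, 5t), B = max(7, 5t) and gap = A - B. The rules coincide once 5t reaches 28, that is at t = 28/5 = 5.6 days. The gap is at its largest, 28 - 7 = 21 days, while 5t is at most 7, that is up to t = 7/5 = 1.4 days. The half-lives below, other than amiodarone's, are illustrative. The last column is the fraction of drug remaining at limit B, 2^(-B/t), assuming first-order elimination.

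| t (days) | A | B | Gap (days) | Remaining at B |
|---|---|---|---|---|
| 1 | 28 | 7 | 21 | 2^-7 = 0.78% |
| 1.4 | 28 | 7 | 21 | 2^-5 = 3.1% |
| 2 | 28 | 10 | 18 | 3.1% |
| 3 | 28 | 15 | 13 | 3.1% |
| 5 | 28 | 25 | 3 | 3.1% |
| 5.6 | 28 | 28 | 0 | 3.1% |
| 58 | 290 | 290 | 0 | 3.1% |

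For a half-life of 1.4 days or less, a last dose 7 to 27 days before Day 1 (27 - 7 + 1 = 21 possible days) satisfies the footnote and breaches Section 6.5.3.1. The reverse cannot happen: anyone who meets A also meets B.

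**Opioid lists.** The prohibited table has 17 + 11 = 28 CYP3A4 substrates and the caution table has 16 + 16 = 32 entries. Alfentanil and fentanyl are the only names in both. Their status, read step by step:

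1. The Appendix 11 prohibited table: labelling says avoid or contraindicated.
2. The Appendix 11 caution table: labelling allows use with caution or dose adjustment. This cannot hold together with step 1 for the same drug.
3. Section 6.5.3.3: avoid, or use with caution. It accommodates either list and does not say which one governs.
4. Section 6.5.2.3: only non-prohibited opioids may continue, so a site needs the answer that step 3 does not give.
5. Exclusion 27: current treatment with a drug prohibited under Section 6.5.3 excludes the participant, so the same uncertainty reaches eligibility.

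**The case against.** The best defence on the washout is that there is no operational conflict. The footnote sets a minimum, Section 6.5.3.1 sets a longer one, and a site can satisfy both. Section 6.5.3.1 uses Appendix 11 only as a source of examples, so harm requires a site to read the appendix alone. This stands as a limit on the consequence, but it does not make the footnote correct. The separate footnotes for inhibitors and inducers could also reflect a deliberate difference. The documents do not settle that, which is why the direction of the fix is left to the sponsor.

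On the opioids, Section 6.5.3.3 covers both outcomes. The dose caps in Sections 6.5.1 and 6.5.2.3, and the warning in Section 6.5.2.3 about stronger opiate effects, manage part of the risk. The drug labels themselves cannot be seen here. All of this stands. What remains is that two notes in one appendix contradict each other about the same two drugs.

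Two stronger readings are tempting, and the documents do not support them.

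- A reader might infer that the shorter washout leaves inhibitor on board at the first dose. Both rules require 5 half-lives, so at most 1/32 = 3.1% remains under first-order elimination.
- A reader might infer from Section 8.11 that a prohibited listing forces study drug to stop. That row first sends the reader to Section 6.5.3 for the specific action. For CYP3A4 substrates this leads to Section 6.5.3.3, which allows caution.

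**Conclusion.** Minor, and wrong as written on both counts. The inhibitor footnote understates the governing washout by 28 - max(7, 5t) days for half-lives below 5.6 days, at most 21 days. Section 6.5.3.1 governs through Section 5.3, so the consequence is a possible eligibility breach at a site that relies on the footnote, not an exposure problem. The size in participants is unknown: the inhibitor list has 48 entries, or 47 drugs without grapefruit juice, which has its own rule, and a half-life is given for only 1 of the 47.

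Alfentanil and fentanyl carry incompatible label statements, and it is unclear whether they count as non-prohibited opioids.

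No sample size, power or alpha figure is touched. The main estimands follow treatment policy, so they do not depend on how these drugs are classified. The conclusion rests on the current protocol text, on randomization and first dose falling on the same day and, for the 3.1% bound only, on first-order elimination.

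**What to change.** 1. In the Appendix 11 inhibitor footnote, replace 7 days with 28 days and keep the alternative of 5 half-lives, whichever is longer. Both rules then equal max(28, 5t) and the gap is 0 for every half-life. If the sponsor intended 7 days for inhibitors, amend Section 6.5.3.1 instead, so that one rule remains.
2. List alfentanil and fentanyl once. The default is to keep them on the prohibited list and delete both from the caution list, unless clinical pharmacology review supports caution. If they stay prohibited, a sentence in Section 6.5.3.3 naming these two opioids as prohibited may be needed, because that section otherwise still allows caution.
3. Do not extend that sentence to every CYP3A4 substrate in the prohibited table. Section 6.5.3.4 does say that use of the listed BCRP substrates "is prohibited within 4 weeks or 5 half-lives (whichever is longer) prior to the Randomization Visit (Visit 2) and during the trial", but copying that wording would change the rule for all 28 listed CYP3A4 substrates, not two. It would move up to 26 others from avoid-or-caution to barred (some, such as tacrolimus and cyclosporine, are already restricted in Section 6.5.4.2). The sponsor should do this only if it intends it and states the wider eligibility effect.

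The cost is two appendix edits and at most one sentence in Section 6.5.3.3, issued as a clarification with a note to sites. Design, sample size and analyses do not change. The downside is slightly stricter eligibility for recent users of short half-life inhibitors, compared with what the footnote alone lets through, and for users of the two opioids.
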